## 10.6. Derived Variables

### 10.6.1. Standardized Scores: Comparison of Individual Scores to Age-Matched Normative Data for [REDACTED] Computerized Cognitive Tests (Age-Adjusted Z-Scores)

A comparison of individual scores to age-matched normative data will also be conducted. The process will be as follows:

- Performance on each neurocognitive outcome measure will be standardized relative to age-matched normative data (i.e., the score will be converted to a z-score by subtracting the age matched mean from the normative sample and dividing by the age-matched standard deviation (SD) from the same normative sample)
- The multiplicand equals 1 for outcome measures for which a higher score is indicative of better cognitive performance and -1 for outcome measures where a lower score is indicative of better cognitive performance. Please see Table 2 for details regarding the multiplicand for each outcome measure.
- The z-score will be calculated as follows:

$$z - Score (z_{ijt}) = \frac{(x_{ijt} - \bar{x}_t)}{SD_t} * Multiplicand$$

Where:

$t$  = is the outcome measure indicator

$i$  = indexes subject  $i$

$j$  = indexes the  $j$ th assessment for subject  $i$

$x$  = cognitive score

$\bar{x}_t$  = mean performance score of the age-matched normative sample for outcome measure  $t$

$SD_t$  = Standard Deviation of the age-matched normative sample for outcome measure  $t$

#### 10.6.1.1. Age-Matched Normative Data for [REDACTED] Computerized Cognitive Tests

Note: These tables are stored in XLS format in nD ID: 004758297.

**Table 3. Detection**

Age (Years)	Mean	SD
4	2.82934	0.12057
5	2.77951	0.11345
6	2.74635	0.09264
7	2.66173	0.09901
8	2.63129	0.13746
9	2.58581	0.13506
10	2.56241	0.08007
11	2.53830	0.07896
12	2.52938	0.07682
13	2.51597	0.07535

14	2.51298	0.08101
15	2.50910	0.07674
16	2.50538	0.07644
17	2.50197	0.07528
18-34	2.45444	0.07337

**Table 4. Identification**

[figure not shown]
Age (Years)	Mean	SD
4	3.01615	0.07030
5	2.94433	0.11321
6	2.94156	0.06801
7	2.87557	0.07695
8	2.84589	0.11548
9	2.80141	0.09222
10	2.76101	0.07096
11	2.73223	0.07068
12	2.71368	0.06719
13	2.69591	0.06782
14	2.68636	0.06954
15	2.67744	0.06687
16	2.67182	0.06561
17	2.66634	0.06456
18-34	2.64200	0.06351

**Table 5. One Back – Speed**

Age (Years)	Mean	SD
6	3.17567	0.06515
7	3.07410	0.11496
8	3.03745	0.11140
9	3.00543	0.11960
10	2.96038	0.09147
11	2.92315	0.08742
12	2.90079	0.08970
13	2.88112	0.08832
14	2.86992	0.08875
15	2.85673	0.08837
16	2.84739	0.08920
17	2.83990	0.09017
18-34	2.78579	0.09418

**Table 6. One Back – Accuracy**

Age (Years)	Mean	SD
6	1.14048	0.23689

7	1.13669	0.20779
8	1.16183	0.23773
9	1.30178	0.18364
10	1.30448	0.14716
11	1.31396	0.14210
12	1.32934	0.14177
13	1.32993	0.13466
14	1.33324	0.13896
15	1.34055	0.13843
16	1.34830	0.13575
17	1.35444	0.13472
18-34	1.39617	0.12998

**10.6.2. Conversion of Scale Outcome Measures into Age-Adjusted Z-Scores**

All primary, secondary, and exploratory outcome measures for scales will need to be converted to z-scores. Outcome measures will be available in one of three forms: standard score, T-score, or scaled score. The Table 7 below defined the general properties of each score form, along with the conversion formula for changing these into z-scores.

**Table 7: Scale Outcome Measure Conversion to Z-Scores**

Score Name	Mean	SD	Z-Score Conversion Formula
Standard Score	100	15	(Standard Score – 100) / 15 * multiplicand
T-Score	50	10	(T-Score – 50) / 10 * multiplicand
Scaled Score	10	3	(Scaled Score – 10) / 3 * multiplicand

**10.6.3. Standardized Scores: Comparison of Individual Scores to eTHINK Hemophilia Normative Data (Hemophilia-Adjusted Z-Scores)**

A comparison of individual scores to eTHINK hemophilia normative data will also be conducted. The process will be as follows:

- Performance on each neurocognitive outcome measure will be standardized relative to eTHINK hemophilia normative data (i.e., the age-adjusted z-score will be converted to a hemophilia-adjusted z-score by subtracting the mean from the eTHINK hemophilia normative sample and dividing by the eTHINK hemophilia normative standard deviation (SD) from the same normative sample)
- The z-score will be calculated as follows:

$$z_{ijt} = \frac{(x_{ijt} - \bar{x}_t)}{SD_t}$$

Where:

$\bar{z}_{ijt}$  = cognitive hemophilia-adjusted z-score

$t$  = is the outcome measure indicator

$i$  = indexes subject  $i$

$j$  = indexes the  $j$ th assessment for subject  $i$

$x$  = cognitive age-adjusted z-score

$\bar{x}_t$  = mean performance score of the eTHINK hemophilia normative sample for outcome measure  $t$

$SD_t$  = Standard Deviation of the eTHINK hemophilia normative sample for outcome measure  $t$

Tables similar to the above Tables 3-6 will be generated based on the eTHINK study and re-used here.

## 11. Data Quality Assurance

### Computerized Tests

Data from the computerized test battery will be collected on iPads at site(s) and uploaded to the database for processing. data management staff will query any data discrepancies. Queries will be confirmed and resolved with the sponsor.

### Traditional Neurocognitive Instruments

Before raters could administer the neurocognitive instruments to subjects, they were required to become certified by completing online training requirements (i.e., didactic training videos and for some scales (Bayley-III, WPPSI-IV, and WASI-II) demonstrations showing proper administration and scoring of the scales). A neuropsychologist at then evaluated the completed source document and audio recording from the practice administration. The neuropsychologist issued corrective feedback, if necessary. During the study, monitored the first Bayley-III, WPPSI-IV, and WASI-II administrations for each rater to ensure quality. For these administrations, raters submitted the source document of their administration. A neuropsychologist at then evaluated the completed source document and issued corrective feedback, if necessary.

#### 11.1. Computerized Test Completion Criteria

For each of the computerized tests, subjects must provide sufficient responses to allow computation of reliable performance measures. For the majority of computerized tests, the term “sufficient” has been defined as a Test Completion criterion. The number of trials required for Test Completion is unique to each test. They do not vary for different patient groups or study samples.

The completion criteria set forth a priori for each test were as follows:

- DET: The number of responses provided by the subject is  $\geq 100\%$  of the desired number of trials (responses  $\geq 35$ )
- IDN: The number of responses provided by the subject is  $\geq 100\%$  of the desired number of trials (responses  $\geq 30$ )
- ONB: The number of responses provided by the subject is  $\geq 100\%$  of the desired number of trials (responses  $\geq 31$ )

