### 9.4. Handling of missing data

No imputations will be performed in the event of missing data due to dropouts or omitted visits. All incomplete subject profiles will be retained in the analysis. In view of issues of reliability, all analyses will be conducted with completion failures removed.

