### **Custom Battery (DET, IDN, ONB; Attention/Processing Speed)**

Clinical assessment of attention usually depends on three sources of information: (1) psychometric tests designed to measure other cognitive functions, (2) specific neuropsychological tests of attention; and direct behavioral observation and measurement. Assessment often requires the clinician to obtain information about performance under different conditions. Measures of attention include attention span, divided attention, switching, response intention and planning, sustained performance and vigilance, and information-processing speed.

Information processing speed along with working memory have been identified as measures of cognitive impairment. While traditionally clinicians assessed with the Paced Auditory Serial Addition Test (PASAT), over the past decade the advent of computerized tests of information processing have been relied on to assess processing speed. The [REDACTED] computerized cognitive test battery proposed for this study includes an assessment of processing speed, attention/vigilance, and working memory.

- [REDACTED] Custom Battery (Peds platform, ages 4-9; Adult platform, ages 10-21)
  - Detection test (processing speed, psychomotor function)
  - Identification test (attention/vigilance)
  - One Back Test (working memory)

*Note: Ages 4-5 years old will be administered with pediatric Detection and Identification. Ages 6-9 years old will be administered with pediatric Detection, Identification, and One Back. Ages 10-21 will be administered with adult Detection, Identification, and One Back.*

Although each of the [REDACTED] computerized cognitive tests yields multiple outcome measures, research by [REDACTED] has identified a set of measures that are optimal for the detection of cognitive change in clinical trials at both the group and individual level (Falleti et al., 2006; Maruff et al., 2009; Bland & Altman, 1996a; Bland & Altman, 1996b).

For each [REDACTED] computerized cognitive test, a single primary outcome measure was selected prior to data analysis from each test in the battery to minimize experiment-wise error rates. Each primary outcome measure was selected because it has been shown to be optimal for the detection of change because:

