Conceptual Reasoning Domain Social Interactions Domain Practical Functioning Domain Adaptive Behavior Domain Score	Communication Skill Area Functional Pre-Academics Skill Area Self-Direction Skill Area Leisure Skill Area Social Skill Area Community Use Skill Area Home Living Skill Area Health and Safety Skill Area Self-Care Skill Area Motor Skill Area	
ABAS Parent 5-21 year old		
Conceptual Reasoning Domain Social Interactions Domain Practical Functioning Domain Adaptive Behavior Domain Score	Communication Skill Area Functional Academics Skill Area Self-Direction Skill Area Leisure Skill Area Social Skill Area Community Use Skill Area Home Living Skill Area Health and Safety Skill Area Self-Care Skill Area	

ABAS Adult 16-89 year old		
Conceptual Reasoning Domain Social Interactions Domain Practical Functioning Domain Adaptive Behavior Domain Score	Communication Skill Area Functional Academics Skill Area Self-Direction Skill Area Leisure Skill Area Social Skill Area Community Use Skill Area Home Living Skill Area Health and Safety Skill Area Self-Care Skill Area	
Detection Identification Attention Domain Composite	Pediatrics 4-5 year old	
Detection Identification One Back (speed) One Back (accuracy) Attention Domain Composite	Pediatric 6-9 year old	
Detection Identification One Back (speed) One Back (accuracy) Attention Domain Composite	Adult 10-21 year old	

[1] Higher scores indicate better performance (multiplicand = +1).

[2] Lower scores indicate better performance (multiplicand = -1).

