### 10.5. Other Outcome Measures

The following composite scores will be computed and analyzed:

- Attention Domain Composite
  - o Peds Age 4-5: DET, IDN speed scores must exist
  - o Peds Age 6-9: DET, IDN, ONB speed scores; at least two of three scores must exist
  - o Ages 10-21: DET, IDN, ONB speed scores; at least two of three scores must exist

The composite scores will be calculated by:

- 1) Standardizing each of the test scores included in the cognitive domains against age-matched US normative population (international normative population for [redacted] computerized tests) data for that test (Section 10.6.1 specifies the procedure for the standardization of the tests for the purposes of creating the Attention Domain Composite score).
- 2) Computing the average of the available standardized test scores if the required number of scores available is met (as described above).

The Attention Domain Composite score is normalized based on age and therefore serves as the age-adjusted z-score in summary tables without any further calculations.

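### The computerised tests are accepted on response count alone and Detection and Identification are scored on speed alone, so a child who taps fast without attending can pass the check and score above the norm.

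*SAP*

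**What the plan says.** **Acceptance.** SAP 11.1 sets the aim that "subjects must provide sufficient responses to allow computation of reliable performance measures" and then gives one criterion per test. For Detection it begins "DET: The number of responses provided by the subject is" (at least 35), for Identification "IDN: The number of responses provided by the subject is" (at least 30) and for One Back "ONB: The number of responses provided by the subject is" (at least 31). None of the three requires a response to be correct.

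**Exclusion.** SAP 9.4 states that "all analyses will be conducted with completion failures removed". For the computerised tests, SAP section 11 adds only the querying of data discrepancies. Neither document gives an accuracy floor, a limit on anticipatory responses or any other integrity rule.

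**Scoring.** SAP 10.5 builds the Attention Domain Composite from speed scores only. For the youngest group the requirement is "Peds Age 4-5: DET, IDN speed scores must exist"; from age 6, One Back speed joins them. In SAP Table 2 the DET, IDN and One Back speed measures carry footnote 2: "Lower scores indicate better performance (multiplicand = -1". SAP 12.2 orients all z-scores so that positive means better.

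**Accuracy.** Table 2 lists an accuracy outcome for One Back only. One Back is not given at ages 4-5 (SAP 10.4), and its accuracy does not enter the composite at any age.

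**The concern.** The completion rule is meant to secure reliable scores, but it checks only that the child kept responding. A child who stops early is removed. A child who taps to the end without attending is kept, and if the taps are quick the result reads as good processing speed and attention.

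The battery is part of a safety evaluation. Protocol 3.4 gives PEG distribution to the choroid plexus as the reason for neurocognitive follow-up, Protocol 8.3.3 requires the attention domain in all countries, and Protocol Table 8-1 starts the computerised battery at age 4. Inattentive or impulsive responding is among the behaviours such follow-up should notice. If it appears as a high z-score, it can mask a decline in that child and raise the group mean in a trial that expects about 40 completers. Under SAP 10.3 a result more than 1 SD above the eTHINK mean goes to the expert panel as a possible gain in function, not as suspect data.

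**Working it through.** The plan states no figure on this point, so there is none to reproduce. The check applies the SAP's own scoring to its own norms.

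**Inputs.** Means and SDs by age from SAP Tables 3 (DET), 4 (IDN), 5 (One Back speed) and 6 (One Back accuracy). Age 4: DET 2.82934 (SD 0.12057), IDN 3.01615 (SD 0.07030).

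**Assumptions.** Speed is in log10 milliseconds and accuracy is the arcsine of the square root of the proportion correct. SAP 10.4 names log10 and arcsine as example transformations but gives no units. The age-4 means back-transform to 675 ms (DET) and 1038 ms (IDN), which are plausible times. The tap times below are illustrative, since the documents give none. The mean is taken as the child's mean over whichever responses are scored.

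**Formulas.** SAP 10.6.1 with multiplicand -1: z = -(log10(RT) - mean)/SD. SAP 10.5: composite = average of the available speed z-scores.

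**Age 4 at 600 ms** (log10 600 = 2.77815):
- DET: (2.82934 - 2.77815)/0.12057 = +0.42
- IDN: (3.01615 - 2.77815)/0.07030 = +3.39
- Composite: (0.42 + 3.39)/2 = +1.91

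**Age 4 at 1000 ms** (log10 1000 = 3):
- DET: (2.82934 - 3)/0.12057 = -1.42
- IDN: (3.01615 - 3)/0.07030 = +0.23
- Composite: (-1.42 + 0.23)/2 = -0.59 (unrounded -0.593)

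**Composite by age and mean tap time, same formulas:**

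| Age | 300 ms | 500 ms | 600 ms | 700 ms | 1000 ms |
|---|---|---|---|---|---|
| 4 | +5.29 | +2.80 | +1.91 | +1.15 | -0.59 |
| 5 | +3.40 | +1.44 | +0.74 | +0.15 | -1.22 |
| 6 | +6.82 | +3.80 | +2.72 | +1.81 | -0.30 |
| 7 | +4.08 | +1.73 | +0.89 | +0.18 | -1.46 |
| 8 | +3.11 | +1.27 | +0.62 | +0.06 | -1.23 |
| 9 | +2.91 | +0.95 | +0.24 | -0.35 | -1.72 |
| 10 | +3.45 | +0.68 | -0.31 | -1.15 | -3.09 |

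The sign depends on tap speed. The composite is zero where log10(RT) = sum(mean/SD)/sum(1/SD). That is about 886 ms at age 4, 728 ms at age 5 and 950 ms at age 6, and about 639 ms at age 9. The two or three tests do not move together: at 600 ms DET is only +0.01 at age 5 and -0.34 at age 6. IDN (+1.47 and +2.40) and, at age 6, One Back speed (+6.10) carry the composite.

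**One Back accuracy if half the answers are correct** (assumed chance level; arcsine of the square root of 0.5 = 0.78540). At age 6: (0.78540 - 1.14048)/0.23689 = -1.50. The same step gives -1.69 at age 7, -1.58 at age 8 and -2.81 at age 9. Against the age norms, these all lie beyond 1 SD on the low side.

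**The case against.** A reader might infer that any child who taps without attending will be scored as improved, so that the plan is biased toward finding no harm. The documents do not support that. Slow inattentive tapping scores as worse, and the effect fades or reverses at older ages and with modestly slower taps. From age 6, guessing would probably lower One Back accuracy enough to count as a possible decrease under the 1 SD rule of SAP 10.3, if the eTHINK values resemble the age norms (they are not given). Nor is it safe to count IDN, One Back speed and the composite at age 6 as three separate high results, because the composite averages the other two with DET.

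Four further points stand in part:
- **Which responses are scored.** The SAP does not say whether the speed score uses all responses or only correct, non-anticipatory ones. A restriction would weaken the effect. If IDN and One Back are two-choice tasks (not stated), correct-only scoring would not remove it, since about half of fast guesses are correct by chance. An anticipation limit could help more.
- **Unseen rules.** Protocol 8.3.3 asks for standardised testing parameters and refers to a neurocognitive manual that is not among the documents. It may hold an integrity rule, but the SAP cites none.
- **Other instruments.** BRIEF-P covers inhibition and working memory from age 2 in all countries, and BASC-3 adds hyperactivity and attention problems in English-speaking countries. The expert panel reviews each child in context. Inattention therefore does not rest on tap speed alone.
- **Weight.** These outcomes are descriptive and are not among the protocol's primary or secondary endpoints. The minima, maxima, listings and per-patient plots of SAP 12.2 would make an extreme score visible. They would not show that it was inaccurate, since no DET or IDN accuracy is specified for display.

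Deleting low-accuracy tests would also be a poor remedy: it could drop the children whose attention has really declined.

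**Conclusion.** The concern holds in a conditional form. The SAP's only validity rule for the computerised tests is a response count, and DET, IDN and the composite reward speed alone. Fast inattentive tapping can therefore be accepted and scored above the norm, or as improved on the child's earlier result. The exposure is greatest at ages 4-5, where no accuracy outcome exists. From age 6, One Back accuracy would probably give a warning, but it screens nothing out and leaves the composite unchanged.

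The size ranges from several SDs above the norm to below it, according to tap time and age. It rests on the assumed log10-millisecond scale and on a speed score that admits fast guesses. No frequency can be given from the documents, so the effect on group means cannot be estimated. This is a cheap improvement to a descriptive safety analysis, not a flaw in the trial's main conclusions.

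**What to change.** In SAP 11.1, keep the completion counts and add:
- **An integrity flag per test, based on accuracy.** Use the test provider's own criterion if there is one, and cite it. Otherwise set an above-chance threshold that suits the test's response format. For instance, if IDN were a two-choice task with 30 scored trials (an assumption), 20 or more correct has probability 0.049 under guessing. DET needs an equivalent condition on valid responses.
- **A definition of the speed score.** State whether only correct responses count and how anticipatory ones are handled.

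In SAP 10.3 and 12.2:
- Tabulate and list DET and IDN accuracy beside speed, and count and list flagged tests.
- Pass the flag to the expert panel, so that a fast, low-accuracy result is not presented as a possible gain in function.
- Report z-scores and the composite with and without flagged tests, and add a sensitivity analysis that treats flagged tests as poor performance. Do not simply delete them.

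The cost is SAP wording, one derivation and a few more tables. SAP section 6 allows revisions before database lock. The accuracy data probably exist already, since SAP 10.4 says that each of the "computerized cognitive tests yields multiple outcome measures", but this should be confirmed with the provider. The downside is that some young children's speed scores will carry a flag. Because flagged scores are kept in one version of the results, comparability with the norms and eTHINK is preserved there.

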## 12. Statistical Methodology

### 12.1. Analysis Overview

All statistical analyses and summary information will be generated according to this Statistical Analysis Plan (SAP). Data collected in this study will be presented using standardized scores, comparing cognitive outcome measures against age-matched norms, hemophilia norms, the most recent prior assessment, and the Initial Assessment.

### 12.2. Analyses

Cognitive outcome measures from the neurocognitive instruments will have a series of z-scores calculated. This includes age-adjusted US normative (international normative for [REDACTED] computerized tests) z-scores (see Section 10.6.1), age-adjusted hemophilia z-scores (see Section 10.6.3), z-score change from prior (for both age- and hemophilia-adjusted z-scores), and z-score change from Initial Assessment (for both hemophilia- and age-adjusted z-scores). The above z-scores will be tabulated descriptively (n, mean, standard deviation, median, interquartile range (first quartile, third quartile), min, max).

Individual domains/scores by visit will be plotted per patient for each instrument.

A subject listing including scores, z-scores (age- and hemophilia-adjusted), change from prior z-scores (age- and hemophilia-adjusted) and change from initial assessment z-scores (age- and hemophilia-adjusted) on each neurocognitive instrument and outcome measure will be generated. All z-scores will be adjusted so that positive scores reflect improvement.

All analyses will be done in SAS (v9.4).

See Appendix 1 for an example of the tables, listing, and figures (TLF).

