8.3.3 Neurocognitive assessments

Neurocognitive assessments should be performed according to [Table 2-1](#), [Table 2-2](#), [Table 8-1](#) and [Table 8-2](#)

The following domains will be assessed in all countries:

- Executive function
- Attention/processing speed/working memory

Further, the following domains will be assessed in English speaking countries (e.g. Australia, Canada, United Kingdom, and the United States):

- Neurodevelopment or cognitive function and intelligence
- Emotional behaviour
- Adaptive behaviour

The timing of the neurocognitive assessments should be planned to allow as much flexibility for the patients as possible and can be made within ± 1 month of the assessment visits, except for the visit 1 and EOT visit where the neurocognitive assessments can be made at the visit date or up to 1 month ahead of the visit. The first assessment should be planned for the visit immediately after the patient turns either 1 or 2 years of age depending on country. Hereafter the visit schedule as found in [Table 8-1](#) and [Table 8-2](#) should be followed except if the next planned assessment visit is within three months of the initial assessment. All assessments should be performed using generally accepted standardised testing parameters to ensure optimal conditions for performance. A description of

Protocol
Trial ID: NN7999-3895
UTN: U1111-1135-9557
EudraCT No.: 2012-004867-38

~~CONFIDENTIAL~~

| | | |
|----------|------------------|---------------------|
| Date: | 05 November 2019 | Novo Nordisk |
| Version: | 8.0 | |
| Status: | Final | |
| Page: | 50 of 119 | |

neurocognitive assessments, training, equipment and related procedures will be provided in the Manual for neurocognitive assessments.

An independent External Expert Review Panel will evaluate the results of the neurocognitive assessments in context of the Structured Developmental History and Haemophilia History for each patient. Information regarding responsibilities, procedures, meeting frequency and workflow to be used by the External Expert Review Panel are specified in the External Expert Review Panel charter.

A CRO will provide the results from the External Expert Review Panel to Investigator as narrative reports including normalised domain scores and categorical assessment. It is the responsibility of the Investigator to report any findings if considered qualifying for an AE. If any findings are present at V0 it should be recorded as medical history.

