Novo Nordisk A/S will be responsible for the statistical analysis.

The main statistical reporting of the trial will be performed when at least 20 patients have completed main phase (minimum 50 weeks) with at least 50 EDs and completed visit 23. Data from patients not yet having completed main phase and data from patients that have entered extension phase at this point will be included up to latest visit prior to this cut-off date. The data will be presented for the main phase and extension phase separately as well as combined. Except for the confidence interval for inhibitor rate and for annualised bleeding rate, the evaluation of data will be based on descriptive statistics, i.e. summary tables, listings and figures.

An updated statistical reporting of the trial with supportive data will be performed when at least 40 patients have had at least 100 EDs. Data from all patients will be included up to latest visit prior this cut-off date. The data will be presented for the main + extension phase and the extended prophylaxis period (beyond 100 EDs) separately as well as combined.

All data will be reported separately in a final report when the trial is completed.

[figure not shown]

Figure 16–1 Individual patient flow and time period for main trial report

Protocol
 Trial ID: NN7999-3895
 UTN: U1111-1135-9557
 EudraCT No.: 2012-004867-38

~~CONFIDENTIAL~~

| | | |
|----------|------------------|---------------------|
| Date: | 05 November 2019 | Novo Nordisk |
| Version: | 8.0 | |
| Status: | Final | |
| Page: | 97 of 119 | |

Multiple bleeding locations occurring from the same event (e.g. due to a fall) or at the same time point will be counted as one bleeding episode.

All bleeding endpoints will be evaluated based on bleeding episodes treated with N9-GP unless the bleeding was considered clinically insignificant (non-treatment requiring bleeding episode) and the associated treatment given was part of prophylaxis.

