16.1 Sample size calculation

No formal sample size calculations have been performed. The sample size of 40 completers is based on EMA guideline⁵.

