### 10.3. Definition of Findings – Initial and Follow-Up

Based on the results from the eTHINK trial (all age groups pooled) the mean and standard deviation (SD) will be calculated for composite scores of all tests (see Table 2 for primary outcome measures). Each patient's individual results from each test (initial and follow-up assessments) from this trial will be compared to the mean and SD from the respective test from the eTHINK trial. If the patient's results are greater than 1 SD above the eTHINK mean (or less than -1 SD below the eTHINK mean), this will be treated as potential increase (or decrease) of the respective neurocognitive function and will be discussed with experts at the external expert review panel (EERP). If the absolute value of change from the eTHINK mean is  $\leq 1$  SD, the change will be categorized as "normal variation" rather than signal. If less than three different test results from the same visit are outside the defined threshold of 1 SD, the result will also be categorized as "normal variation", but still discussed with experts during the EERP.

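### The group-mean neurocognitive z-scores have no confidence interval, and the only written signal rule, applied child by child, barely separates a uniform 0.5-SD fall from no effect

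*SAP*

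**What the plan says.** Protocol Section 3.4 explains why these data are collected: PEG reached choroid plexus cells in animals, and the consequences of long exposure are not fully known. SAP Section 7 sets an objective about outcomes in exposed patients.

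For the group, SAP Section 12.2 states: "The above z-scores will be tabulated descriptively (n, mean, standard deviation, median, interquartile range", followed by the minimum and maximum. This covers the age-adjusted and haemophilia-adjusted z-scores and their changes from the prior and Initial Assessments. Protocol Section 16 is consistent with it: "Except for the confidence interval for inhibitor rate and for annualised bleeding rate, the evaluation of data will be based on descriptive statistics".

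For the individual child, SAP Section 10.3 singles out a result if "results are greater than 1 SD above the eTHINK mean (or less than -1 SD below the eTHINK mean". Within that band, "the change will be categorized as 'normal variation' rather than signal". A visit gets the same label "If less than three different test results from the same visit are outside the defined threshold of 1 SD", although it is still discussed by the panel. Protocol Section 8.3.3 describes that panel: "An independent External Expert Review Panel will evaluate the results of the neurocognitive assessments in context of the Structured Developmental History and Haemophilia History", patient by patient.

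The SAP text states no interval, margin or reading rule for a group mean.

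**The concern.** A drug effect on development might appear as a modest shift in every child rather than as a few extreme children. The natural measure of such a shift is the mean z-score with its uncertainty. The plan prints the mean without the uncertainty, and its one formal rule addresses individuals.

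False reassurance is the main risk. Bayley-III/WPPSI-IV/WASI-II, ABAS-3 and BASC are given in English-speaking countries only (SAP Table 1), and the main report can be triggered by 20 completers (Protocol Section 16). A mean near zero from a dozen children looks like good news, and nothing obliges the report to say how large a decline remains compatible with it. The inhibitor rate, by contrast, has an exact upper confidence limit (Protocol Section 16.3).

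**Working it through.** There is no figure in the plan to reproduce: "No formal sample size calculations have been performed. The sample size of 40 completers is based on EMA guideline", and nothing is stated on precision for the neurocognitive outcomes.

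**Assumptions.** Haemophilia-adjusted z-scores are normal with SD 1. The shift δ is 0 or −0.5 SD for every child; 0.5 is illustrative and does not come from the documents. Results within a visit share a common correlation r, taken as 0.5 and varied from 0 to 0.7. Each Table 2 primary outcome counts as one result; the SAP does not define a test result for this count.

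**Step 1: one result.** P(outside) = Φ(−1 − δ) + 1 − Φ(1 − δ).
- δ = 0: 15.9% + 15.9% = 31.7% (before rounding).
- δ = −0.5: Φ(−0.5) + 1 − Φ(1.5) = 30.9% + 6.7% = 37.5% (before rounding).

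The low tail nearly doubles, but the loss of high results cancels much of the gain.

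**Step 2: three or more results outside at one visit.** Given a shared factor F ~ N(0,1), p(F) = Φ((−1 − δ − √r·F)/√(1−r)) + 1 − Φ((1 − δ − √r·F)/√(1−r)). The binomial tail P(B(k, p(F)) ≥ 3) is then averaged over F. Outcome counts k come from Protocol Tables 8-1 and 8-2 and SAP Table 2. Cells show r = 0.5, with the range for r = 0 to 0.7.

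| k | Source of the outcomes | δ = 0 | δ = −0.5 |
|---|---|---|---|
| 4 | All countries, age 2:0–3:11: BRIEF-P | 15% (10–20%) | 22% (15–26%) |
| 7 | All countries, age 4:0–5:11: BRIEF-P 4, computerised battery 3 | 37% (36–39%) | 46% (43–53%) |
| 16 | English-speaking, age 4:0–5:11: those 7, WPPSI-IV 2, BASC-3 3, ABAS-3 4 | 77% (61–92%) | 81% (67–97%) |

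Small batteries mostly stay below the count and large ones mostly exceed it, with or without a shift. If each instrument counted once, a child with one or two instruments could never reach three.

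**Step 3: what an interval on the mean would show.** Half-width = t(n−1, 0.975)/√n, treating the eTHINK mean as known.
- n = 40: 2.023/6.325 = 0.32
- n = 20: 2.093/4.472 = 0.47
- n = 12: 2.201/3.464 = 0.64

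With an observed mean of zero, the interval excludes a 0.5-SD fall at n = 18 (2.110/4.243 = 0.497) but not at n = 17 (2.120/4.123 = 0.514). If the true shift is −0.5, the chance that the interval excludes zero is 87% at n = 40, 56% at n = 20 and 29% at n = 10 (noncentral t).

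**Step 4: eTHINK sampling error.** With M eTHINK children, the normal approximation is 1.96·√(1/n + 1/M). M is not in the documents. For M = 100 to 500, the half-width at n = 40 is 0.37 to 0.32, and the chance of excluding zero under a 0.5-SD shift is 76% to 86%.

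**Step 5: change from Initial Assessment.** The SD of change is √(2(1−ρ)) for within-child correlation ρ: 1.00, 0.77 and 0.63 at ρ = 0.5, 0.7 and 0.8. At n = 20 the half-widths are 0.47, 0.36 and 0.30.

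**The case against.** The case for leaving the plan alone has several sound parts.

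- **The mean is not hidden.** Mean, SD and n are tabulated against both norms, so a mean near −0.5 would be visible and a reader could compute a simple interval. That stands. It would not include eTHINK error, though, and it leaves the reading unplanned.
- **Individual safeguards exist.** The panel reviews each patient, visits under the three-result count are still discussed, trajectories are plotted, and developmental, cognitive or behavioural events are medical events of special interest. All true, but each works on individuals.
- **Descriptive reporting is a design choice.** Neurocognition is not among the objectives and endpoints in Protocol Section 4. An interval can still be descriptive.
- **The table shells may already show one.** SAP Appendix 1 is not in the supplied text, and CI is in the abbreviation list. If so, the SAP text should say it.

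A reader might infer that a uniform 0.5-SD fall would usually be read as no signal. The documents do not support that. Nothing says the child labels decide the group conclusion, and with 16 outcomes about 81% of shifted visits exceed the count.

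A reader might also test the share of flagged children and quote its low power: 15%, 15% and 4% for 4, 7 and 16 outcomes at n = 40, r = 0.5, one-sided 2.5%. No such test is planned, and those figures come from pooling both tails. Counting only visits with at least three results below −1 SD, the share moves from 7.1% to 19.5%, 16.8% to 37.4% and 34.5% to 60.4%, with power of about 69%, 79% and 88%.

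**Conclusion.** The concern holds as a gap in precision and reporting. The plan has no interval for either group mean, and the individual rule discriminates poorly whichever battery is used: at r = 0.5 the visit-level difference is 4 to 9 percentage points. It cannot serve as a group-level conclusion, and the SAP does not say that it should.

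The practical consequence is that a near-zero mean from roughly 17 children or fewer could be presented without disclosing that a 0.5-SD fall is not excluded. How many children will have the English-only instruments is not stated.

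The result rests on normality, SD 1, equal correlation, an illustrative shift and counting by primary outcome. An interval measures sampling error only. It does not make eTHINK a concurrent control or turn Initial Assessment into a pre-treatment baseline, and it cannot rescue a small n; it shows the limit.

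**What to change.** In SAP Section 12.2, for each Table 2 primary outcome, add two-sided 95% confidence intervals for (a) the mean haemophilia-adjusted z-score, with the sampling error of the eTHINK mean included, and (b) the mean change from Initial Assessment. Label them descriptive, without multiplicity adjustment. Require the report to state, beside each mean, the size of decline that the interval does not exclude. Extend the exception in Protocol Section 16 to these intervals. Keep SAP Section 10.3 for the panel's individual review, and say that it is not the group-level conclusion.

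A fixed pass/fail margin is not needed. The documents give no basis for −0.5 SD. With no drug effect, a rule that the lower limit must lie above it would fail for a given outcome about 13% of the time at n = 40 (100% − 87%) and 44% at n = 20 (100% − 56%). The sponsor may justify a margin if it wants one.

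The cost is SAP wording, a line in the protocol and extra columns in planned tables; no new data or patients. SAP Section 6 allows revision before database lock. The downside is that wide intervals in small subsets read less favourably than a bare mean.
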